Participants in this study are patients with hypotension, who have undergone evaluation as part of our “The Pathophysiology of Orthostatic Hypotension” protocol (IRB#030752, CRC approval pending). Based on the results of these studies, we will administer medication which we believe might improve their symptoms. We will first test a single dose of one or more drugs with monitoring for 24 hours. A drug or drugs effective at preventing an orthostatic fall in blood pressure might then be tested in a 5-day crossover trial with comparison of effects to placebo. Based on the results of the 5-day trial, a patient might then be given a 2-month trial of the drug, with periodic admissions to the GCRC for assessment of symptoms. The period of time needed to complete this study will depend on the number of medications tested.

Drug withdrawal

Participants must remain off any medications that could affect blood pressure for three days prior to and during study. This includes not only their usual scheduled medications, but also other drugs that might be taken intermittently. If their symptoms are severe enough that they or their physician have concerns that their symptoms may worsen, they may be admitted to the hospital for observation during this portion of the study. While they are an inpatient on the GCRC, their general condition, blood pressure and heart rate will be checked regularly to reduce any risk.

Urine pregnancy test

We will perform a urine pregnancy test every time female participants are admitted to the hospital for this study.

Diet

We will ask study participants to eat a standard diet with no caffeine, 150-mEq/day sodium, 70 mEq potassium, and no substances that interfere with catecholamine synthesis, release or assay for three days prior to and during testing.

24-Hour Urine Collection

Participants will collect their urine for 24 hours every time they are admitted to the hospital for this study. The urine will be analyzed for sodium, potassium, creatinine, and catecholamines.

Orthostatic vital signs

Orthostatic vital signs will be measured several times a day. This testing consists of blood pressure and heart rate measured while patients are lying down and then repeated after standing quietly for 5 minutes, using the Dinamap.

Single-dose drug trials

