Participants will be admitted to the Vanderbilt Clinical Research Center the evening prior to the study. In the morning, the patients will be seated or in bed for a 30 min baseline period of blood pressure and heart rate monitoring. The medication will be given by mouth, and blood pressure and heart rate will be monitored every 10-15 minutes for the first hour, using a Dinamap. Orthostatic vital signs will be taken after 1, 2, 3, 4, 8, and 12 hours. Fifteen ml of blood will be collected through a saline lock during baseline and after 2, 4, and 8 hours while in the supine and standing positions to measure catecholamines (total of 4 samples lying down and 4 samples upright). Aldosterone will also be measured in blood collected during baseline and at one other timepoint, depending on the duration of the drug effect (total of 2 samples lying down and 2 samples upright). A second blood sample will be collected with the aldosterone and an aliquot of plasma frozen for possible analysis of plasma renin activity. Urine will be collected from 0-7 hours, 7-12 hours and 12-24 hours for measurement of catecholamines. Depending on how well the drug is tolerated and the degree of improvement in orthostatic vital signs and symptoms following the drug, another single-dose drug trial might be scheduled 48 hours after the first or the patient might be asked to start a 5-day trial of the drug at that time. If they are not scheduled for another trial at this time, they can be discharged. The medications include domperidone, metyrosine, L-DOPS, alpha-methyldopa, L-dopa, carbidopa, atomoxetine, and placebo.

Single-dose trial

Time	Days 3,2 pre-study	Day 1 pre-study	Study Day							
			0 hr	1 hr	2 hr	3 hr	4 hr	8 hr	12 hr	24 hr
Drug/diet restriction	X	X	X	X	X	X	X	X	X	X
Urine collection		X	X	X	X	X	X	X	X	X
Admission to GCRC		X								
Pregnancy test		X								
Drug administration			X							
Blood sample			X				X	X	X	
Vital signs		X	X	X	X	X	X	X	X	

5-Day drug trials

Once the appropriate dose has been decided, we will conduct a single-blinded crossover trial. Depending on where they live and the severity of their symptoms, participants might be able to go home

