for part of this study. However, after 4 days on the drug (or placebo), they will be admitted to the GCRC. They will be supine and NPO after midnight. In the morning, we will do a Posture Study to determine the effectiveness of the treatment. Before breakfast, we will draw 15 ml of blood while they are supine and another 15 ml after they have stood for 30 minutes to measure catecholamines and aldosterone. A second blood sample will be collected with the aldosterone and an aliquot of plasma frozen for possible analysis of plasma renin activity. We will monitor blood pressure and heart rate during this study, using a Dinamap. Standing time will be determined, and the participants will be asked about their symptoms periodically during the study. For at least three days following this testing, participants will take no medication. They will then start a 5-day regimen of the medication, if they previously took the placebo, or placebo, if they previously took the medication. They will not be told whether they are taking active drug or placebo. The Posture Study will be repeated in the GCRC after the second 5-day period.

5-day trial

Time	Day 3 pre-study	Days 1,2 pre-study	Study day 0	Study days 1,2,3		Study day 4	Study day 5	Study days 6,7		Study day 8	Study days 9,10,11			Study day 12	Study day 13
Drug/diet restriction	X	X	X	X	X	X	X	X	X	X	X	X	X	X	X
Urine collection						X								X	
Admission to GCRC						X								X	
Pregnancy test	X														
Drug/placebo administration			X	X	X	X				X	X	X	X	X	
Posture study/Blood sample							X								X
Vital signs						X	X							X	X

Depending on the results of the 5-day trial, participants will be given a longterm trial of a drug. At the initiation of treatment, and after two weeks, four weeks, and eight weeks of drug, they will be evaluated by a posture study, 24-hour urine collection and assessment of their symptoms. The dose of the medication will be adjusted after two and four weeks of treatment if there has been insufficient improvement in blood pressure (able to stand with < 20 mmHg decrease in systolic blood pressure) or symptoms.

Chronic trial

Days	-3,-2	-1	0	1-10	11,12	13	14	15-24	25,26	27	28	29-52	53,54	55	56
Restrict diet	X	X	X		X	X			X	X	X		X	X	X
Collect urine		X				X				X				X	
Admit to GCRC		X				X				X				X	
Pregnancy test		X				X				X				X	
Take Drug			X	X	X	X	X	X	X	X	X	X	X	X	
Posture study/ Collect blood			X				X				X				X
Vital signs		X	X			X	X			X	X		X	X	X
Adjust dosage							X				X				

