BIOSTATISTICS

Statistical analyses will be performed on a personal computer with the statistical package SPSS for Windows (Version 10.0, SPSS, Chicago). Some paired comparisons (Paired t-test, Wilcoxon signed-rank test, repeated measures ANOVA, Friedman ANOVA by ranks) might be needed to compare treatment responses within a subject.

Protection of Human Subjects:

POPULATION:

The conduct of these studies will involve approximately 25 human subjects. Subjects will include patients with severe orthostatic hypotension and other autonomic symptoms who do not meet criteria for one of our standard diagnoses. Potential study participants will first take part in "The Pathophysiology of Orthostatic Hypotension" (IRB #030752, CRC approval pending). Results from that study will provide information on the pathophysiology of the autonomic disorder and might suggest which medication(s) might be an effective treatment. Subjects will range in age from 18-70 and be non-smokers, drug-free, able to give informed consent, and free of pulmonary, renal, hematopoietic, hepatic and cardiac disease. Exclusion criteria for the study include smoking, pregnancy, medications affecting the autonomic nervous system, any chronic illness, and anemia (Hct<35).

RESEARCH MATERIALS:

Research materials include blood, urine, and data. The blood will be analyzed for catecholamines, renin and aldosterone. Urine will be analyzed for catecholamines, sodium, potassium, and creatinine.

RECRUITMENT OF SUBJECTS:

We will recruit patients from those referred to the physicians of the Autonomic Dysfunction Center at Vanderbilt who have participated in "The Pathophysiology of Orthostatic Hypotension" (IRB #030752, CRC approval pending). In each instance, the investigator will describe the complete protocol to the prospective participant. The subjects will then be given a written informed consent form that has been approved by the Vanderbilt Institutional Review Board. The subject will be given adequate time to read the consent form, ask questions, and if satisfied by the responses, sign the form. Consent or refusal to participate in this study will not affect medical care. No modifications or waiver of the elements of consent have been authorized, nor will any be necessary in the execution of this study.

POTENTIAL RISKS:

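### The paired tests listed in BIOSTATISTICS, if used for the 5-day two-period crossover, leave out the period effect; one sentence adding a period term would correct this

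*Combined protocol and SAP*

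**What the plan says.** Experimental Design and Methods states that a drug effective in single-dose testing "might then be tested in a 5-day crossover trial with comparison of effects to placebo". Under 5-Day drug trials the design is given as follows: "Once the appropriate dose has been decided, we will conduct a single-blinded crossover trial". At the end of the first period, "In the morning, we will do a Posture Study to determine the effectiveness of the treatment". Then "For at least three days following this testing, participants will take no medication", and after that "They will then start a 5-day regimen of the medication, if they previously took the placebo, or placebo, if they previously took the medication". Finally, "The Posture Study will be repeated in the GCRC after the second 5-day period". The 5-day schedule puts the two Posture Studies on study days 5 and 13.

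Either treatment can therefore come first. The documents do not say how order is assigned, or that the two orders will be balanced.

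BIOSTATISTICS gives the whole analysis plan in one sentence: "Some paired comparisons (Paired t-test, Wilcoxon signed-rank test, repeated measures ANOVA, Friedman ANOVA by ranks) might be needed" for comparing treatment responses within a subject. It names no trial stage and no period, sequence or carryover term. Biostatistical Support, under Justification for GCRC Utilization, adds that no data analysis is anticipated.

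**The concern.** In a two-period crossover, each patient's drug-minus-placebo difference contains the treatment effect plus or minus whatever changed between the two test days. A one-sample paired test treats all these differences as draws from one distribution, although the two order groups have different means whenever there is drift.

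Some drift is plausible on the protocol's own account. The second Posture Study comes eight days after the first, with drug and diet restrictions running throughout. Potential Risks warns of temporary worsening after medication is stopped, and of a few days of headache and fatigue after caffeine is stopped.

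At stake is the group-level estimate from the only stage with a described placebo crossover and participant blinding. It may be shifted towards or away from the drug, or carry an interval wider than the data warrant.

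**Working it through.** The plan states no SD, effect size, alpha or power, so it has no figure to reproduce.

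**Inputs from the documents.** Two periods, either order, one Posture Study per period; about 25 subjects in the whole study. Only some of them enter the crossover, so 25 is an upper bound for its N.

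**Assumed inputs.** SD of the within-patient difference 15 mmHg; drift (period 2 minus period 1, apart from treatment) of 4, 8 or 10 mmHg; order split 18:7 or 13:12, with placebo-first the larger group; two-sided alpha 5%; no carryover.

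**Algebra.** Let τ be the drug effect, π the drift, s the SD, and n_P and n_D the numbers taking placebo first and drug first.
- Mean drug-minus-placebo difference: τ + π (placebo first), τ − π (drug first).
- Bias of the paired mean: π(n_P − n_D)/N. At 18:7 this is 11/25 = 0.44π; at 13:12 it is 1/25 = 0.04π.
- Paired-test SE divided by the correct SE for that estimate: √[1 + (π/s)² · 4·n_P·n_D/(N(N−1))]. The last factor is 504/600 = 0.84 at 18:7 and 624/600 = 1.04 at 13:12. The correct SE is 15/√25 = 3.0 mmHg.

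**Results.** Bias and SE ratio come from the formulas. Type I error and power come from simulation with 20,000 or more trials per setting.

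| Split | Drift (mmHg) | Bias (mmHg) | SE ratio | Type I error, paired t | Power at 9 mmHg, paired t |
|---|---|---|---|---|---|
| 18:7 | 4 | 1.8 | 1.03 | about 8% | not compared |
| 18:7 | 8 | 3.5 | 1.11 | about 15% | not compared |
| 18:7 | 10 | 4.4 | 1.17 | about 19% | not compared |
| 13:12 | 4 | 0.16 | 1.04 | about 4% | 82% |
| 13:12 | 8 | 0.32 | 1.14 | about 3% | 77% |
| 13:12 | 10 | 0.40 | 1.21 | about 2% | 74% |

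Paired-test power at 18:7 is left out because the bias would flatter it. Reversing the split to 7 placebo-first and 18 drug-first gives a bias of the same size and opposite sign.

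The period-adjusted estimate is the average of the two order-group means, with pooled within-group SD and N − 2 degrees of freedom. It has no bias and a type I error of about 5% in every row. Its power at 13:12 is 82% whatever the drift.

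**The other listed tests.** Simulations at other splits (12:12, 8:16, 5:20) show the signed-rank test departing from 5% in the same way. With 8 drug-first and 16 placebo-first and a drift of half an SD, for example, its type I error is 8.3%, against 8.6% for the paired t-test. Repeated measures ANOVA with treatment as the only factor and two conditions is the paired t-test (F = t²).

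**The case against.** Several points on the other side stand.

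- **The plan does not commit to these tests for the crossover.** They "might be needed to compare treatment responses within a subject", with no stage named. Friedman's test would suit several single-dose trials, and repeated measures ANOVA could carry a period factor. The point is therefore conditional: it applies if the listed tests are used on the crossover as they stand.
- **A reader might infer that the bias corrupts entry to the 2-month trial.** The documents do not support that. They make entry a decision about each patient, based on that patient's results, and a group-level period term does not alter it.
- **A reader might also infer that false positives are inflated however order is assigned.** They are not. If order came from an independent coin toss, the paired t-test would keep about 5% on average over allocations (5.0% and 5.2% in simulation at N = 25). The inflation is conditional on an unequal realised split. The bias given that split remains.
- **The size is assumed.** At 4 mmHg and 13:12 the effect is negligible. Crossover N may be far below 25, with seven active drugs listed and only some patients progressing. At N = 6 split 2:4, with SD 15 and drift 8 mmHg, type I error is 4.2%, not inflated, though the estimate is still off by 8 × 2/6 = 2.7 mmHg.
- **The design limits drift.** Restrictions start three days before dosing, so the first Posture Study already follows about eight restricted days. Both tests use the same unit, and patients have already had repeated standing measurements in the single-dose stage.

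These points limit the size and reach of the concern. They do not remove it, because nothing in the documents balances the orders or puts period into the analysis.

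**Conclusion.** The concern holds in conditional form. Applied to the 5-day crossover, the paired t-test, the signed-rank test and a treatment-only repeated measures ANOVA ignore any period effect. The estimate is then biased in proportion to drift and order imbalance. With near-equal orders the error is one of conservatism: intervals too wide and power lost, not false positives.

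Under the assumptions above, the consequence runs from negligible (4 mmHg, 13:12) to a bias of 4.4 mmHg with type I error near 19% (10 mmHg, 18:7). Where a real trial would fall in that range cannot be settled from the documents. The point concerns the group-level estimate in a study whose analysis wording is tentative. It is a worthwhile and cheap improvement, not a flaw that invalidates the trial.

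**What to change.** Add one sentence to BIOSTATISTICS: outcomes of the 5-day crossover will be analysed in a model with patient, treatment and period. An equivalent is to compare the period 2 minus period 1 differences between the two order groups, by t-test or, for the non-parametric version, by rank-sum test. Report the number of patients in each order. Visits, measurements and enrolment do not change.

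The cost is one degree of freedom, plus some power in two situations:
- **Very unequal orders without drift:** at 18:7 the SE rises from 3.0 to ½ × 15 × √(1/18 + 1/7) = 3.34 mmHg, and power for 9 mmHg falls from 82% to 73%. At 13:12 there is essentially no loss.
- **Very small N:** at 3:3 with no drift and an assumed 20 mmHg effect, power falls from 74% to 69%.

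If every patient took the same order, period and treatment would be confounded and the model could not be fitted. A period term also does not deal with carryover, which is a separate question.

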Treatment of Orthostatic Hypotension

NCT00581477

Protocol and Statistical Analysis Plan

November 14, 2003

**CLINICAL RESEARCH CENTER
VANDERBILT UNIVERSITY
PROJECT PROPOSAL #1288**

**Project Title: The Treatment of Orthostatic Hypotension
The Treatment of Orthostatic Hypotension**

Project Number:

IRB Approval Number: 030750

IRB Approval Date: November 14, 2003

Principal Investigator: [name]., Professor of Medicine, Pharmacology and Neurology

Co-Investigator(s): [name]., Division of Clinical Pharmacology
[name], Division of Cardiology
[name], Departments of Medicine and Pharmacology
[name], Division of Clinical Pharmacology
[name], Division of Cardiology
[name], Division of Clinical Pharmacology

HYPOTHESIS

We propose that a systematic trial of medications in patients presenting with a unique and chronic constellation of symptoms of autonomic dysfunction will provide us with information on the pathophysiology of their condition and assist us in optimizing their treatment.

SPECIFIC AIMS

To give a single dose of one or more drugs to determine the effect on orthostatic hypotension in a group of patients with autonomic dysfunction of unknown pathophysiology. Depending on the results of these single-dose trials, we might subsequently do 5-day trials and chronic (approximately 2 months) trials.

BACKGROUND AND SIGNIFICANCE

Norepinephrine (NE) and epinephrine (E) are critical determinants of blood pressure. Moreover, they are also involved in the regulation of autonomic outflow in the brainstem and spinal cord. In the periphery, NE is pressor, but within the central nervous system (CNS) it often depresses sympathetic outflow, resulting in a fall in blood pressure. Thus, any factor that alters the synthesis of these catecholamines can perturb blood pressure at several interacting levels. Tyrosine hydroxylase [(tyrosine to L-dihydroxyphenylalanine (DOPA)] is the rate-limiting step in NE synthesis under almost all circumstances. DOPA decarboxylase converts DOPA to dopamine (DA). Dopamine- β -hydroxylase (DBH) converts DA to NE. Loss of DBH leads to an inability of the neuron to synthesize NE, resulting in a buildup of DA.

In 1986, we, and independently, colleagues in Rotterdam, reported a syndrome in which patients have a congenital absence of the DBH enzyme. Results of a battery of biochemical and physiological tests in DBH-deficient patients helped us to identify the pathophysiology of these patients and enabled us to design an effective treatment.

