Occasionally, patients present to the Autonomic Dysfunction Center with a unique constellation of

symptoms of autonomic dysfunction so that they do not fit into a diagnostic category (Orthostatic Intolerance, Pure Autonomic Failure, Multiple System Atrophy, Baroreflex Failure). Some of these patients have severe orthostatic hypotension and resemble those with DBH deficiency, but they do not have the extreme plasma levels of DA. We propose that medication trials in these patients will assist us in optimizing their treatment. Evaluation will be undertaken under controlled conditions with medication and dietary restrictions and will consist primarily of orthostatic blood pressure and heart rate measurements and plasma catecholamine determinations.

Participants will first take part in a study designed to provide information on the pathophysiology of their autonomic problems (The Pathophysiology of Orthostatic Hypotension, IRB#030752, CRC approval pending). Results from this study will help us determine which drug(s) to administer in the proposed protocol.

PRELIMINARY STUDIES

Once the pathophysiology of DBH deficiency was understood, we were able to rapidly develop a specific and effective therapy. Consistent with DOPA and DA reducing blood pressure, the administration of a tyrosine hydroxylase inhibitor, such as metyrosine, raises blood pressure in DBH-deficient individuals. The pressor effect appears to correlate with the metyrosine-associated reduction in plasma DA and DOPA levels and also urinary DA levels. DOPS, or Droxidopa INN:(-)-threo-3-(3, 4-dihydroxyphenyl)-L-serine, is structurally closely related to NE, but has an additional COOH group. It can be pumped up into the noradrenergic nerves and converted into NE by L-aromatic amino-acid decarboxylase without requiring DBH. L-DOPS has been used effectively in the treatment of patients with complete DBH deficiency. It might also improve the blood pressure in patients that have profound orthostatic hypotension but do not appear to have complete DBH deficiency.

EXPERIMENTAL DESIGN AND METHODS

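### If repeated-measures ANOVA or Friedman is used to compare three or more single-dose treatments, only patients given every compared treatment count; a linear model on all test days avoids this

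*Combined protocol and SAP*

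**What the plan says.** BIOSTATISTICS names the paired t-test and the Wilcoxon signed-rank test, then "repeated measures ANOVA, Friedman ANOVA by ranks) might be needed to compare treatment responses within a subject". It does not assign a test to the single-dose, 5-day or chronic stage, and it has no rule for patients who did not receive every treatment being compared.

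SPECIFIC AIMS puts the group question at the single-dose stage: "To give a single dose of one or more drugs to determine the effect on orthostatic hypotension in a group of patients".

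Treatment sets at that stage differ by design:
- The list has eight entries: "The medications include domperidone, metyrosine, L-DOPS, alpha-methyldopa, L-dopa, carbidopa, atomoxetine, and placebo" (Single-dose drug trials).
- Choice follows a prior work-up: "Results from this study will help us determine which drug(s) to administer in the proposed protocol" (end of BACKGROUND AND SIGNIFICANCE).
- Whether a further test follows rests on tolerance and response to the one before: "another single-dose drug trial might be scheduled 48 hours after the first" (Single-dose drug trials).
- JUSTIFICATION FOR GCRC UTILIZATION says that the number of medication trials varies between patients. Under Biostatistical Support it adds that no data analysis is anticipated.

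**The concern.** The paired t-test and Wilcoxon compare two treatments. Repeated-measures ANOVA and Friedman are therefore the only listed methods for three or more. In conventional form both need a complete row for each patient, so a patient missing one compared treatment drops out entirely.

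A comparison of several drugs at the single-dose stage could then rest on very few of about 25 unusual patients. The remaining test days would still guide each patient's care and serve two-treatment pairs, but they would add nothing to that comparison.

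**Working it through.** The plan gives no power, significance level, effect size or standard deviation, so it has no figure to reproduce. Everything below is conditional on stated assumptions.

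**Inputs.** About 25 patients (POPULATION); eight treatments (Single-dose drug trials); *k* single-dose tests per patient, which the documents do not fix.

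**1. Plausible range for *k*.** OTHER SUPPORT requests 700 aldosterone assays: 700/25 = 28 per patient. A single-dose test uses 4 (two lying, two upright). A 5-day crossover uses 2 posture studies × 2 = 4. A chronic trial uses 4 × 2 = 8 if it is sampled the same way, which the text does not state.
- One crossover and one chronic trial: (28 − 4 − 8)/4 = 4 tests.
- Two crossovers and one chronic trial: (28 − 8 − 8)/4 = 3.
- One crossover only: (28 − 4)/4 = 6.
- No later stage: 28/4 = 7.

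This is an inference from requested quantities. The 84 pregnancy tests for 12 expected women give 84/12 = 7 admissions each. That fits *k* = 4 as 1 + 2 + 4 only if all four single-dose tests share one admission and the crossover counts as two, whereas the 5-day table marks one pregnancy test.

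**2. Patients with placebo and two named drugs.** For random subsets the expected number is 25 × C(5, k−3)/C(8, k). If placebo is always one of the *k*, it is 25 × C(5, k−3)/C(7, k−1). At *k* = 4 these are 25 × 5/70 = 1.8 and 25 × 5/35 = 3.6.

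| Tests per patient | 3 | 4 | 5 | 6 | 7 |
|---|---|---|---|---|---|
| Random subset | 0.4 | 1.8 | 4.5 | 8.9 | 15.6 |
| Placebo always given | 1.2 | 3.6 | 7.1 | 11.9 | 17.9 |

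Choices may instead concentrate on *m* treatments including these three. At *k* = 4 the count is then 25 × (m−3)/C(m, 4): 25 × 3/15 = 5 for *m* = 6, 25 × 2/5 = 10 for *m* = 5, and 25 for *m* = 4.

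**3. What few complete patients means.** The smallest exact Friedman p for three treatments and *n* patients is (1/6)^(n−1): 0.167 at *n* = 2 and 0.028 at *n* = 3. At *k* = 4, the chance of fewer than three complete patients is 0.74 for random subsets (Binomial(25, 1/14)), 0.29 if placebo is always given (Binomial(25, 1/7)), and 0.10 if choices concentrate on six treatments (Binomial(25, 1/5)).

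**4. Model against complete sets.** Simulated standard error of one drug-minus-placebo contrast, with assumed within-patient SD 10, between-patient SD 15, placebo always given, and at least one complete patient for the complete-set estimate:
- *k* = 3: 11.7 to 5.2.
- *k* = 4: 8.3 to 3.9, a fall of 1 − 3.9/8.3 = 53%.
- *k* = 6: 4.1 to 3.1, a fall of 24%.
- *k* = 4 with patient-by-drug SD 15: 12.4 to 6.9, a fall of 44%.

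**5. Model against pairs.** Average standard errors in SD units, order fitted, patient fixed, between-day correlation 0.5, no patient-by-drug variation:
- Random subsets: 0.405 v 0.657 (38% lower) at *k* = 3; 0.322 v 0.464 (31%) at 4; 0.244 v 0.277 (12%) at 6; 0.222 v 0.232 (4%) at 7.
- Placebo always given: 0.368 v 0.391 (6%) at *k* = 3; 0.288 v 0.313 (8%) at 4.

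The spread of simulated estimates shows a slightly larger gap at *k* = 4 (3.9 v 4.4, or 11%, without order terms), because allocations with few pairs weigh more. With patient-by-drug variation, placebo always given and *k* = 4, model v pairs was 5.3 v 5.4 at patient-by-drug SD 10. At SD 15 two runs gave 6.8 v 6.5 and 6.9 v 6.8. With placebo randomly omitted, the gain persisted at SD 10: 5.8 v 8.1 (28%).

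**6. Selection.** With drugs chosen for patients expected to respond to them (true average effect 15, patient-by-drug SD 10), fixed-patient and random-patient models both gave about 21.7.

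**The case against.** The strongest reply is that the plan never commits to this use. BIOSTATISTICS is hedged, no passage states a group comparison of three or more single-dose treatments, and Biostatistical Support anticipates no analysis. Single-dose results mainly steer each patient's next step. Both tests suit data that are complete by design, such as the repeated readings within a test ("Orthostatic vital signs will be taken after 1, 2, 3, 4, 8, and 12 hours") or the chronic-trial visits. All of this stands, and it makes the point conditional. A reader might infer that the plan prescribes a complete-case analysis, or that most patients will be discarded. The documents support neither: they assign no test to a stage, and the complete-set count could be anything from below one to 25. What survives is that the group aim sits at the single-dose stage, and no other multi-treatment method or rule for incomplete sets is given.

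A second reply is that the listed paired tests already use every patient given both treatments. This largely stands for two-treatment questions when placebo is always given. It does not cover a joint comparison of several drugs, or contrasts where placebo was often omitted.

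A third is that random subsets contradict the plan's own targeted choice. That is correct. The counts illustrate a range and do not forecast the loss.

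**Conclusion.** The point holds in conditional form. If repeated-measures ANOVA or Friedman is applied to three or more single-dose treatments, the comparison is confined to patients given all of them, and this design can make such patients scarce. Under random subsets they average 1.8 to 3.6 of 25 at four tests and 8.9 to 11.9 at six. The four-test figure is itself only inferred from the assay request.

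The main gain from a model on all test days is over the complete-set tests: the standard error is roughly halved at four tests under the stated assumptions. Against paired tests with placebo always given, the average gain is about 6 to 9% at three to four tests, and it can vanish or slightly reverse if drug effects vary between patients, which the protocol's premise makes plausible.

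A reader might also infer that the model cures selection. It does not: where drugs are chosen by expected benefit, its estimates apply to the patients selected for each drug. This is an optional, low-cost improvement.

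**What to change.** 1. For single-dose comparisons of three or more treatments, specify a linear model on all test days with treatment, test-day order and patient as fixed effects. The outcome should be one summary per test day of the lying-to-standing systolic fall, chosen before the data are seen. A random-patient version is an optional sensitivity analysis.
2. Keep the paired t-test and Wilcoxon for two-treatment comparisons. Keep repeated-measures ANOVA or Friedman for complete sets: time points within a test, and chronic-trial visits.
3. Label each estimate exploratory and as applying to patients selected for that drug. State that patients with one test day add nothing to the within-patient contrasts.
4. Reconcile the Biostatistical Support statement with SPECIFIC AIMS and BIOSTATISTICS.

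The cost is analysis wording only, with no change to schedule or sample size. Treating patient as fixed costs about 1 to 8% in standard error against a random-patient model at three to four tests (assumed correlations 0.3 to 0.7). It also requires treatments to be linked through shared patients. In an illustration where testing stopped after a good response, the fixed-patient model understated a true 0.8 SD effect by 0.05 to 0.09 SD. Where severity drove drug choice and there was no true effect, it stayed within 0.006 SD of zero, while the random-patient model erred by 0.05 to 0.14 SD. That contrast is the reason to consider the sensitivity analysis.
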